3.5. Population excluded from Safety Analysis

Population excluded from safety analysis will be reported separately with descriptive analysis only (number, percentage of subjects with adverse events and number of adverse events). However, subjects who have not been administered for INLYTA® will be excluded from this analysis set.

4. Study Endpoints

4.1. Safety Endpoints

The clinical nature, incidence, duration, and severity of adverse events; discontinuation due to adverse events; outcome and possible causality will be monitored in this study.

4.2. Efficacy Endpoints

- Tumor response based on RECIST 1.1
- Objective Response Rate (ORR)

ORR will be defined as the number of subjects who achieve a best overall response of complete response (CR) or partial response (PR), divided by the total number of subjects in efficacy analysis set.

- Progression-free survival (PFS)

PFS is defined as the time from first dose of study medication to first documentation of objective tumor progression, or to death due to any cause, whichever occurs first.

- Time to progression (TTP)

TTP is defined as the time from the first dose of study medication to objective tumor progression excluding death.

5. General Consideration

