## **3. RESEARCH METHODS**

### **3.1. Study design**

Observational, non-interventional drug and multi-center study in which subjects will be administered as part of routine practice at Korean health care centers by accredited physicians. At least 3000 subjects should be enrolled in this study based on the Article 6 of “Basic Standards for the Re-examination of New Medicines” notified by MFDS. However, with additional 3 years of study period, at least 100 subjects who are being treated with Inlyta within the approved indication will be studied for total of 9 years according to the review result by the MFDS per Pfizer’s request to adjust the number of subjects. The study can be performed in Korean health care centers where INLYTA® is prescribed for advanced renal cell carcinoma (aRCC) after failure of one prior systemic therapy which is the indication for INLYTA® and where post-marketing study is allowed by institutions.

To achieve the target sample size, the study is being conducted in prospective study design and retrospective study design.

Patients to whom INLYTA® is first administered or patients who are already on INLYTA® during the study period should be enrolled in the study. Observation should be done from treatment initiation of INLYTA® for at least 28 calendar days. There are no visits or activities mandated by this study and routine observation will be done during INLYTA® treatment.

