### **Confirmation of Tumor Response**

Confirmation of response is required for non-randomized trials with primary endpoint of response, but is not required in randomized studies since the control arm serves as appropriate means of interpretation of data.

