### **Best overall response**

The best overall response is determined once all the data for the patient is known. Best response in trials in which confirmation of complete or partial response is not required (ie, randomized trials) is defined as the best response across all time points (for example, a patient who has SD at first assessment, PR at second assessment, and PD on last assessment has a best overall response of PR). When SD is believed to be the best response, it must also meet the protocol specified minimum time from baseline. If the minimum time is not met when SD is otherwise the best time point response, the patient's best response depends on the subsequent assessments. For example, a patient who has SD at first assessment, PD at second and does not meet minimum duration for SD, will have a best response of PD. The same patient lost to follow-up after the first SD assessment would be considered inevaluable.

When confirmation of CR and PR is required (ie, non-randomized trials with primary endpoint of response), the best overall response is defined according to the tumor response along the study. Complete or partial responses may be claimed only if the criteria for each are met at a following time point as specified in the protocol (generally 4 weeks later). In this circumstance, the best overall response can be interpreted as in Table 2.

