3.2. Efficacy Analysis Set

Efficacy analysis set will be included subjects to whom INLYTA® is administered INLYTA® at least once. Subjects who are excluded from the safety analysis set shall be excluded from the efficacy analysis set.

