5.1. Analysis Principles

Statistical analysis will be conducted after database is locked and performed using SAS software version 9.4 or higher according to this statistical analysis plan (SAP). If statistical analysis methods are changed, it will be described in the final clinical study report.

Continuous variables will be summarized by the descriptive statistics (number (n), mean, standard deviation (SD), median, minimum and maximum). Categorical variables will be presented in frequency and percentage (with the percentage excluding the number missing in the denominator).

In case of statistical hypothesis testing, two-sided tests will be conducted at a 5% significance level and the p-value of each test result will be presented in the summary table.

Statistical Analysis Plan for rPMS

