Factor	Classification	Sub-group 1	Sub-group 2	Total
		(N=xxx) n(%)	(N=xxx) n(%)	(N=xxx) n(%)
Best overall response	Objective response rate (ORR)†	xxx(xx.xx)	xxx(xx.xx)	xxx(xx.xx)
	Complete response (CR)	xxx(xx.xx)	xxx(xx.xx)	xxx(xx.xx)
	Partial response (PR)	xxx(xx.xx)	xxx(xx.xx)	xxx(xx.xx)
	Stable disease (SD)	xxx(xx.xx)	xxx(xx.xx)	xxx(xx.xx)
	Progressive disease (PD)	xxx(xx.xx)	xxx(xx.xx)	xxx(xx.xx)
	Not evaluable (NE)	xxx(xx.xx)	xxx(xx.xx)	xxx(xx.xx)
	Not done (ND)	xxx(xx.xx)	xxx(xx.xx)	xxx(xx.xx)
	Total	xxx(xx.xx)	xxx(xx.xx)	xxx(xx.xx)

Sub-group 1: Subjects who are first administered INLYTA® during the study period

Sub-group 2: Subjects who has continued administration of INLYTA® since the time prior to the contract date

†ORR: The numerator is: number of subjects who achieves a best overall response of CR or PR

The denominator is: number of subjects in the efficacy analysis set

Dummy Table

[Table 27] Summary statistics for progression-free survival

Factor	Classification	Number of subjects n(%)
Event rate	Event	xxx(xx.xx)
	Progressive disease	xxx(xx.xx)
	Death	xxx(xx.xx)
Censored rate	Censored	xxx(xx.xx)
PFS time (day)	75th percentile [95% CI]	xx.xx[xx.xx, xx.xx)
	50th percentile [95% CI]	xx.xx[xx.xx, xx.xx)
	25th percentile [95% CI]	xx.xx[xx.xx, xx.xx)

[figure not shown]
Programming note: This table is repeated for each sub-group with the following table title and footnote.

Title : [Table 27-x] Summary statistics for progression-free survival (sub-group x: N=xxx)

Footnote: Sub-group 1: Subjects who are first administered INLYTA® during the study period

Sub-group 2: Subjects who has continued administration of INLYTA® since the time prior to the contract date

[Figure 1] Kaplan-Meier curve for progression-free survival

Programming note: This table is repeated for each sub-group with the following table title and footnote.

Title : [Figure 1-x] Kaplan-Meier curve for progression-free survival (sub-group x: N=xxx)

Footnote: Sub-group 1: Subjects who are first administered INLYTA® during the study period

Sub-group 2: Subjects who has continued administration of INLYTA® since the time prior to the contract date

Dummy Table

[Table 28] Summary statistics for time to progression

Factor	Classification	Number of subjects n(%)
Event rate	Progressive disease	xxx(xx.xx)
Censored rate	Censored	xxx(xx.xx)
TTP time (day)	75th percentile [95% CI)	xx.xx[xx.xx, xx.xx)
	50th percentile [95% CI)	xx.xx[xx.xx, xx.xx)

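### Never-scanned patients count as non-responders in the ORR factor analyses (Tables 29-31), which do not show how many were scanned

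*SAP*

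**What the plan says.** **Denominator.** SAP 4.2 counts subjects with a best overall response of CR or PR, "divided by the total number of subjects in efficacy analysis set". SAP 6.3 item 2 repeats the formula, and the footnote to dummy Table 26 says "The denominator is: number of subjects in the efficacy analysis set".

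**Who is in the set.** SAP 3.2: "Efficacy analysis set will be included subjects to whom INLYTA® is administered INLYTA® at least once". It then narrows the set: "Subjects who are excluded from the safety analysis set shall be excluded from the efficacy analysis set". No baseline or follow-up scan is required.

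**Scans.** Protocol 3.1: "There are no visits or activities mandated by this study". Tumour assessments are recorded when they happen in routine care (Protocol 3.5.4.10).

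**Unassessed subjects.** Table 26 has separate rows for not evaluable and not done. SAP 6.3 item 1 lists CR, PR, SD, PD and NE, but not the not-done category. The general rule in SAP 5.1 is that percentages are calculated "with the percentage excluding the number missing in the denominator".

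**Where the outcome is reused.** SAP 6.3 items 4 and 5 test ORR against demographic and baseline factors at the two-sided 5% level and fit a logistic regression. Tables 29 and 30 show, per factor level, the number of subjects, the ORR with its interval, and a p-value. Table 31 shows coefficients, odds ratios and p-values. None of the three shows how many subjects were assessed.

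**The concern.** A subject without a post-baseline scan can never enter the numerator but stays in the denominator. Observed ORR at any factor level is therefore the share scanned multiplied by the response rate among those scanned. If scan coverage differs between levels, the planned test and odds ratio mix that difference with any difference in response.

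Coverage could plausibly differ in this study. Duration of administration is one of the factors in Table 30, and a patient who stops before a first scan cannot be a responder under this definition, so part of that association is built in. Inpatient status could act in the same way. Data on patients already on treatment are collected only to the extent available (Protocol 3.5.4), so coverage may also differ between the two sub-groups.

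At stake is the reading of Tables 29-31 in the re-examination report: a factor may be reported as affecting response when it affects only whether anyone looked.

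**Working it through.** The plan states no expected ORR, scan rate or power, so there is no figure to reproduce. The sample size of at least 100 is a regulatory minimum (Protocol 3.6).

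**Inputs from the documents:** the ORR formula; no scan schedule; N of at least 100; two-sided 5% tests; chi-square unless expected counts are small.
**Assumed:** share scanned *s*, response rate among scanned patients *p*, and 50 patients per factor level.

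**1. Overall rate.** ORR = *s* × *p*.

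| *p* | *s* = 100% | 90% | 80% | 70% | 50% |
|---|---|---|---|---|---|
| 20% | 20% | 18% | 16% | 14% | 10% |
| 30% | 30% | 27% | 24% | 21% | 15% |
| 40% | 40% | 36% | 32% | 28% | 20% |

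Each 10 points of unscanned patients costs 2, 3 or 4 points of ORR. For scale, 27/100 has an exact 95% interval of 18.6% to 36.8%, so the 3-point shift at 90% scanned is small against sampling error.

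**2. Factor test, equal *p* at both levels.** With p1 = s1 × p, p2 = s2 × p and m their mean:

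- SE0 = √(2m(1−m)/50)
- SE1 = √(p1(1−p1)/50 + p2(1−p2)/50)
- rejection probability ≈ Φ((|p1−p2| − 1.96·SE0)/SE1)

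Worked case, *p* = 30%, 95% versus 60% scanned: p1 = 0.285, p2 = 0.18, m = 0.2325, SE0 = 0.0845, SE1 = 0.0838. This gives Φ((0.105 − 0.1656)/0.0838) = Φ(−0.72) = 0.235.

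| *p* | 95% vs 60% scanned: ORR | rejects | 90% vs 70% scanned: ORR | rejects |
|---|---|---|---|---|
| 20% | 19.0% vs 12.0% | 15.9% | 18% vs 14% | 7.8% |
| 30% | 28.5% vs 18.0% | 23.5% | 27% vs 21% | 10.4% |
| 40% | 38.0% vs 24.0% | 32.6% | 36% vs 28% | 13.4% |

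The nominal rate is 5%. The smallest expected cell is 50 × 0.155 = 7.75, so the SAP rule selects chi-square throughout. In the worked case the unadjusted odds ratio is (0.285/0.715)/(0.18/0.82) = 0.399/0.220 = 1.82, where equal response among scanned patients would give 1.

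**3. What a reader can undo.** Suppose Table 26 shows 20 responders, 8 not evaluable and 12 not done out of 100 (assumed). The reader can compute 20/100 = 20%, 20/88 = 22.7% without the not-done subjects, or 20/80 = 25% without both. Tables 29-31 offer no such route, because the not-done count is not split by factor level.

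**4. Assessed subjects only.** With *p* = 30% and *s* = 80%, the rate is 24/80 = 30% (95% interval 20.3% to 41.3%) beside the planned 24/100 = 24% (16.0% to 33.6%). In step 2 both levels would then have expected rate *p*.

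**5. Stable-disease minimum and confirmation.** Appendix 4 says of SD that "it must also meet the protocol specified minimum time from baseline", and the protocol sets no such time. In Appendix 4 Table 2 that minimum only ever decides between SD and PD or NE. All three are non-responses kept in the denominator, so its effect on ORR is zero. Confirmation does matter: in six of the eleven rows (CR or PR followed by SD, PD or NE) a first response no longer counts if unconfirmed.

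**The case against.** The strongest reply is that this is a deliberate convention. Protocol 3.9.2 calls the efficacy group intent-to-treat, the SAP states the same denominator in three places, and scoring unassessed patients as non-responders is a common conservative choice. Table 26 shows the counts needed to recompute the overall rate. The specific ORR formula can be read as overriding the general percentage rule in SAP 5.1, with not done treated as a category and not as missing. SAP 5.2.1 also promises to evaluate the impact of missing data. For the overall ORR this reply stands, and the planned rate should stay. It does not reach Tables 29-31, where the counts are absent, and SAP 5.2.1 names no method.

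A reader might also infer four stronger points, which the documents do not support:

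- **That ORR reflects scanning practice as much as response.** This depends on the unscanned share, which is not given. At 90% scanned the shift is 2 to 4 points.
- **That Appendix 4 requires confirmed responses here.** It says confirmation "is not required in randomized studies since the control arm serves as appropriate means of interpretation of data", and requires it for non-randomised trials with response as the primary endpoint. This study is not randomised, but names no primary endpoint; its objective is usage and adverse events. It fits neither case. A confirmed rate would also depend more on local scanning, since a responder without a later evaluable scan loses that status.
- **That the unset SD minimum distorts ORR or inflates disease control.** Its effect on ORR is zero, and no disease-control endpoint is planned.
- **That the denominator is every dosed patient, or that ORR is the headline result.** Safety-set exclusions (SAP 3.1) remove some dosed subjects, and ORR is one of four unranked efficacy endpoints.

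**Conclusion.** The point holds in a limited form. The overall ORR is a recoverable, conservative figure. The factor tests and logistic regression on ORR are not recoverable in the same way and can attribute to response what is only a difference in scan coverage. Under assumed 30% response and 50 patients per level, false significance is about 10% at 90% versus 70% scanned and about 24% at 95% versus 60%; across response rates of 20% to 40% the range is about 8% to 33%. All of these rest on assumed scan rates, response rates and equal group sizes, and on a normal approximation. If scan coverage turns out similar across factor levels, the problem largely disappears, but the planned tables would not let a reader see that.

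**What to change.** Keep the planned ORR and add:

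1. **Table 26:** ORR among subjects with at least one post-baseline tumour assessment, for each sub-group and the total.
2. **Tables 29-30:** the number and share of subjects assessed at each factor level.
3. **SAP 6.3 items 4-5:** repeat Tables 29-31 in assessed subjects as a sensitivity analysis, beside and not in place of the planned one.

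Three minor clarifications: label the ORR as unconfirmed; list not done among the categories in SAP 6.3 item 1 and state that the ORR formula takes precedence over the percentage rule in SAP 5.1; and set the minimum SD time that Appendix 4 refers to, which changes only the SD, PD and NE rows.

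The cost is a few extra rows and tables. Assessment dates and overall responses are already on the CRF (Protocol 3.5.4.10), so no new data are needed. The drawback is that the assessed set drops patients who stopped before a scan and may therefore look optimistic, which is why it should only accompany the planned analysis.

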#### **3.5.4.1. Reporting of the study**

Final study report will include analysis for patients prescribed with INLYTA® for the first time, for patients who are already on INLYTA® at the time of enrollment, and for all enrolled patients.

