3.1. Safety Analysis Set

Safety analysis set will be included all subjects who have been administered INLYTA® at least once and evaluated with safety-related endpoints at least once.

The case below shall be excluded from the safety analysis set in the following order:

- 1) Subjects who have been already completed for INLYTA® prior to the contract date.
- 2) Subjects who have not been administered INLYTA®.
- 3) Subjects who have not met the inclusion/exclusion criterion.
- 4) Subjects who have not been evaluated for any safety-related endpoints.
- 5) Subjects who have any significant protocol violation.

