3.4. Sub-Group Analysis Set

Sub-group analysis will be conducted for safety analysis set and efficacy analysis set for:

- Sub-group 1: Subjects who are first administered INLYTA® during the study period
- Sub-group 2: Subjects who has continued administration of INLYTA® since the time prior to the contract date

Statistical Analysis Plan for rPMS

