6.3. Efficacy Analyses

Efficacy analyses will be performed based on data of efficacy analysis set.

- 1) Best overall response [Complete response (CR), Partial response (PR), Stable disease (SD), Progressive disease (PD), Not evaluable (NE)] will be presented in frequency and percentage.
- 2) Objective response rate (ORR) will be presented in frequency and percentage.

Objective response rate (ORR)

$$= \frac{\text{Number of subjects who achieves a best overall response of CR or PR}}{\text{Number of subjects in the efficacy analysis set}}$$

Statistical Analysis Plan for rPMS

- 3) Kaplan-Meier curve for time-to-event endpoints will be generated and presented quartiles with 95% CI, event rates and censor rates. Date of death is date of resolution of serious adverse event in which the category of seriousness is 'Results in death'. In case subjects do not have an event, censor of time-to-event is performed at the date of final follow-up.
 - Progression-free survival (PFS)
 - Time to progression (TTP)
- 4) Objective response rate (ORR) by demographic and other baseline characteristics
 - Objective response rate and 95% CI will be presented by categorical variables of demographic and other baseline characteristics.
 - To identify statistically significant difference in objective response rate by categorical variables of demographic and other baseline characteristics, Chi-square test (χ^2 test) or Fisher's exact test (if the expected frequency for each cell under 5 is more than 20%) will be performed.
- 5) Analysis of factors that affect the efficacy
 - In the re-examination report, logistic regression or multivariate analysis will be performed and an odds ratio with 95% CI and p-value will be presented to identify the factors that affect objective response rate in demographic and other baseline characteristics.

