6.4. Sub-Group Analyses

The following analyses will be performed for subjects who are prescribed with INLYTA® for the first time and for subjects who are already on INLYTA®, separately.

- 1) [6.2. Safety Analyses] - 1) ~ 4)
- 2) [6.3. Efficacy Analyses] - 1) ~ 5)

7. Reporting Conventions

Continuous variables will be summarized by descriptive statistics including n, mean, SD, SE, median, minimum and maximum, and categorical variables will be presented in frequency and percentage. Summary statistics including mean, SD, SE, median, minimum and maximum, etc. will be reported to two decimal places using rounding off.

The p-values through the statistical test will be reported to four decimal place and if p-values smaller than 0.0001 will be written as '<0.0001'.

8. Attachments

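### PFS and TTP run from first dose under plain Kaplan-Meier, but pre-contract starters count only if not finished with INLYTA at the contract date, so the pooled and Sub-group 2 curves are biased upward

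*SAP*

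**What the plan says.** SAP 4.2 sets the origin: "PFS is defined as the time from first dose of study medication to first documentation of objective tumor progression", or to death from any cause. TTP has the same origin and leaves death out. SAP 6.3 item 3 specifies Kaplan-Meier curves and quartiles for both, with one censoring rule: "In case subjects do not have an event, censor of time-to-event is performed at the date of final follow-up".

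New users and patients already on treatment are both eligible (SAP 2.3.1). The first exclusion in SAP 3.1 is "Subjects who have been already completed for INLYTA® prior to the contract date". SAP 3.2 extends it: "Subjects who are excluded from the safety analysis set shall be excluded from the efficacy analysis set". Sub-group 2 in SAP 3.4 is made up of patients whose treatment continued across the contract date.

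Protocol 3.5.4.1 requires results for new users, "for patients who are already on INLYTA® at the time of enrollment, and for all enrolled patients". SAP 6.4 repeats the efficacy analyses for new users and "for subjects who are already on INLYTA®, separately". Tables 27 and 28 and Figures 1 and 2 follow that layout.

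Neither document mentions delayed entry, a landmark or a conditional reading of these curves. The limitations in Protocol 3.12 do not raise the matter.

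**The concern.** A patient who started before the contract enters the analysis only by still being on drug at the contract date. If treatment usually stops at progression, that patient could not have been seen to progress and stop in the pre-contract months. Plain Kaplan-Meier still counts those months as time at risk. Patients with the same start date who progressed and stopped early are absent. The denominators are too large, the hazard too low and the curve too high. Reviewing charts back to the first dose does not help, because it adds history for included patients and cannot restore the excluded ones.

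The pooled and Sub-group 2 PFS and TTP results in the final report would therefore favour the drug. Selection is on drug use rather than on freedom from progression, so some earlier progressions are captured in patients treated past progression. That weakens the bias without removing it.

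The separate Sub-group 1 curve would be a safeguard only if the sub-groups were cut cleanly, and they are not.

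**Working it through.** **1. Plan figure.** There is none to reproduce. The minimum of 100 subjects is a regulatory number (SAP 2.4). The documents state no expected median, start window, prevalent share or lag from contract to consent. All sizes below are conditional on assumptions.

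**2. Direction.** Kaplan-Meier multiplies terms 1 − d(t)/n(t). With truncation, n(t) should count only subjects with entry < t ≤ exit. The plan counts everyone with 0 < t ≤ exit, so n(t) is too large wherever some subjects have not yet entered.

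**3. Closed-form check for Sub-group 2.** Assume exponential PFS with true median 6 months, λ = ln 2/6 = 0.1155. Time from first dose to contract is uniform over W = 24 months, and treatment stops at progression. End of follow-up is ignored.

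- Share included: (1 − e^(−λW))/(λW) = (1 − 0.0625)/2.773 = 0.338.
- For t ≤ W, plain Kaplan-Meier estimates S*(t) = 1 − [1 − (1 + λt)e^(−λt)]/(1 − e^(−λW)).
- At 12 months: 1 − (1 − 2.386 × 0.25)/0.9375 = 0.57, against a true 0.25.
- Setting S* = 0.5 gives (1 + x)e^(−x) = 0.531, so x = 1.58 and t = 1.58/0.1155 = 13.7 months, against a true 6.

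A simulation of 400,000 subjects with follow-up to 36 months after contract gave 0.34, 0.57 and 13.7. Delayed entry gave a median of 6.0 and S(12) = 0.25.

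**4. Dependence on how treatment ends** (plain Sub-group 2 median in months, true median 6):

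| Treatment ends | W = 6 | 12 | 24 | 60 |
|---|---|---|---|---|
| at progression or death | 8.8 | 11.3 | 13.7 | 14.5 |
| also for other reasons | 8.7 | 10.7 | 11.9 | 12.1 |
| a mean of 3 months past progression | 7.2 | 9.0 | 11.2 | 12.1 |
| independently of PFS | 6.0 | 6.0 | 6.0 | 6.0 |

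Delayed entry returns 5.9–6.1 in every cell.

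**5. Trials of 100 subjects.** The grid used W from 6 to 60 months, 25–75% already on drug, 0–50% treated past progression for a mean of 6 months, a signature lag after contract with mean 0, 3 or 6 months, and follow-up to 36 months after contract.

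| Scenario | Plain pooled | Plain Sub-group 2 | Pooled, delayed entry |
|---|---|---|---|
| True median 6, whole grid | 6.3–12.2 | 7.4–14.6 | 5.8–6.2 |
| True median 6, middle case | 8.8 | 12.0 | 5.95 |
| True median 9, whole grid | 9.2–18.3 | 10.4–21.9 | 8.5–9.3 |

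- Middle case (W = 24, 50% prevalent, 25% past progression): root mean squared error of the pooled median is 3.0–3.1 plain and 1.1 with delayed entry.
- Low case (W = 6, 25% prevalent, half past progression): the pooled shift is 0.3–0.4 month. One standard error is 1/(λ√100) = 0.87. Root mean squared error is 0.90–0.97 plain and 0.88–0.98 with delayed entry, so there is no gain.
- If patients must be on drug at enrolment, a mean of 3–6 months after contract, the middle case becomes 9.7–10.2 pooled and 14.0–15.1 in Sub-group 2.

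**6. The sub-group cut.** Three reference points are in use.

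- SAP 3.4: "Sub-group 1: Subjects who are first administered INLYTA® during the study period". Protocol 3.5.1 starts that period on 22 Aug 2012.
- SAP 3.4 cuts Sub-group 2 at the contract date. Protocol 3.5.4 uses the same date to identify first-time users.
- Protocol 3.5.4.1 and 3.5.4.9.1 cut at enrolment.

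A patient who started after approval but before contract meets both SAP definitions. One who started after contract but before enrolment is Sub-group 1 in the SAP and already on drug under Protocol 3.5.4.1. That patient carries the same immortal time.

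For Sub-group 1 alone (n = 50, true median 6), the plain median is 5.8–5.9 if all enrol at first dose. It is 6.0–7.3 if 25–50% enrol a mean of 1–6 months later. Delayed entry brings the latter to 5.9–6.1.

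**The case against.** **Already disclosed.** The sub-groups are tabulated separately, and the footnotes say that Sub-group 2 continued treatment across the contract date. This is fair for Sub-group 2, where the remedy is little more than a clearer label. It leaves the pooled curve uncorrected and relies on a split that the text does not define cleanly. Protocol 3.5.4 supports a contract-date reading of Sub-group 1, but SAP 3.4 and the enrolment wording still disagree with it.

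**The size is not anchored.** Approval was on 22 Aug 2012 and data collection was planned from Dec 2012 (Protocol Appendix 3). At the earliest contracts, post-approval use could therefore span only about 4 months. With that window and half treated past progression, the plain pooled median is 6.05–6.15 for a true 6, and correction gains nothing. This holds for the earliest contracts only; later contracts allow longer windows, and the 60-month case needs contracts from about Aug 2017. The point about anchoring stands: the mechanism is certain and the size is not.

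**Follow-up may be short.** The documents promise limited follow-up and at least 28 days of observation. In the middle case the Sub-group 1 median was not reached in 42% of simulated trials with 6 months of follow-up after entry, and in all of them with 1 or 3 months. This limits the proposed main curve. It does not rescue the plan, because the plain pooled median rises to 10.1 at 6 months and 13.3 at 3 months. Delayed entry stays near 6 but is imprecise (root mean squared error 2.2 at 3 months, 4.4 at 1 month).

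**Too heavy for a descriptive endpoint.** The objective is usage and adverse events, and no test is planned on PFS or TTP. That keeps the point among secondary results, but a reported median should still estimate what its label says.

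**Conclusion.** The concern holds. Followed as written, the plan gives upward-biased pooled and Sub-group 2 curves for PFS and TTP whenever stopping INLYTA is associated with progression or death. The bias disappears only if treatment duration is unrelated to PFS, which is implausible for a cancer drug.

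Under the stated assumptions the pooled median is inflated by anything from 0.3–0.4 month to about double a true median of 6. Start window, prevalent share and treatment past progression drive that range. Confidence is high for mechanism and direction and conditional for size. The plan should be corrected before the final analysis, but only secondary, descriptive results are affected.

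**What to change.** 1. **Sub-groups.** In SAP 3.4, 6.1.6 and the table footnotes, define Sub-group 1 as first dose on or after the site contract date and Sub-group 2 as first dose before it. Reconcile this with the enrolment wording in Protocol 3.5.4.1 and 3.5.4.9.1. Make Sub-group 1 the main PFS/TTP curve, with delayed entry for anyone enrolled after first dose; it is free of this bias only with that adjustment.
2. **Pooled estimate.** Add to SAP 6.3 item 3: *PFS and TTP are measured from first dose. Each subject enters the risk set at the latest of first dose, site contract date and date of the signed document that conditions enrolment. Subjects who progressed before entry are excluded from this estimate and their number is reported.* Name that document: the informed consent (inclusion criterion 3) or the data privacy statement (Protocol 3.5.4, 3.5.4.2, 4.2). Keep the plain pooled curve only as a labelled sensitivity result.
3. **Sub-group 2.** Show the plain curve, labelled as conditional on still being on drug at the contract date. Do not rely on a delayed-entry median from time zero, since few subjects are at risk early. In the middle case its SD is 2.8–3.8 months against 1.7 plain, and the curve reaches zero before the true median in 3–9% of trials.

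**Cost.** SAP wording and a start–stop data layout, with no new visits. Signature dates may have to be taken from the forms, because the listed CRF item is a yes/no box (Protocol 3.5.4.2).

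Subjects leaving the pooled estimate, per 100 at true median 6, for a mean signature lag after contract of 0, 3 or 6 months:

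| Case | Lag 0 | Lag 3 | Lag 6 |
|---|---|---|---|
| Whole grid | 0–19 | 6–34 | 10–42 |
| Middle case | 7 | 18 | 25 |

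If subjects must be on drug at enrolment, 8–9 leave in the middle case. Early confidence intervals widen. With a 60-month window, 75% prevalent and half past progression, the SD of the pooled median is 1.3–1.6 months against 1.3 plain.
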